Daily hunger questionnaire scores will be recorded on a daily basis, prior to the patient's morning meal. If the patient is unable to assess their own hunger due to impaired cognitive function, a parent/caregiver assessment of hyperphagia (PWS-FPD) will be completed instead (see Appendix 11 5 2). During the Screening Period, the patient must complete the daily hunger questionnaire in the electronic diary at least four of the seven days prior to V2. Subjects who do not meet this requirement should not be randomized into the study. V2 may be rescheduled if needed to fulfill this requirement.

Rhythm Pharmaceuticals, Inc. Statistical Analysis Plan, Protocol RM-493-023 29 October 2020, Version 3.0

[figure not shown]
9 Global lunger questions (Appendix 11-5) will be asked an Screening, and Questions I and 2 will then be asked as specified in the SOA once doing has been initiated (Day 1). The Parent Caregiver Global Hunger and the should be used when the patient is unable to assess their own hunger.

Table 2 Schedule of Assessments: 14-Week Open-Label Treatment (Period 3) and Early Termination Visit

	14-Week Open-I (Peri	Label Treatment od 3)	
Visit Number (V)	V14	V15 (EOS)	
Study Week	60	66	Early Termination
Study Day	414	462	Visit
Archive sample for storage ¹		Χţ	
Comprehensive skin exam ²		Х	Х
Fitzpatrick scale		X	Х
Pregnancy test ³	Χţ	X†	X†
Study drug administration/dispense4	X	X	
Daily hunger questionnaire7	← Dai	ily† ——→	Х
Global hunger assessment ⁸		X†	X†
Concomitant medications review	Х	X	X
Nutritional counselling and monitoring		X	

[†] Assessment/sample should be performed/obtained prior to administration of study drug.

¹ Extra retain samples will consist of 2 serum and 2 plasma (K2EDTA) vacutainer tubes and two 5ml urine tubes.

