1.3.5. Efficacy, Parameters

A summary of these endpoints outlining the Analysis Set (population), age limitations, details of the pre-specified baseline, and other pertinent details is found in Table 3.

The primary efficacy endpoint is the proportion of patients (\geq 12 years of age) who achieve a \geq 10% reduction from baseline in body weight after \sim 52 weeks of treatment in the Full Analysis Set (FAS) population.

[figure not shown]
The following 3 endpoints have been identified as key secondary efficacy endpoints.

- Mean percent change from baseline in body weight (in patients ≥12 years of age after ~52 weeks of treatment in the FAS population.
- Mean percent change from baseline in the weekly average of the daily hunger score (in patients \geq 12 years of age) after \sim 52 weeks of treatment in the FAS population.
- The proportion of patients who achieve a ≥25% improvement in the weekly average of the daily hunger score (in patients ≥12 years of age) after ~52 weeks of treatment, in the FAS population.

18

Other secondary endpoints include:

- Mean percent change from baseline in body weight (in patients ≥12 years of age) at the Week 14 visit after treatment with setmelanotide as compared with placebo in the ~14 Week Placebo-controlled Analysis Set (PCS) population.
- Mean percent change from baseline in the weekly average of the daily hunger score (in patients ≥12 years of age) at the Week 14 visit after treatment with setmelanotide as compared with placebo in the PCS population.

Rhythm Pharmaceuticals, Inc. Statistical Analysis Plan, Protocol RM-493-023 29 October 2020, Version 3.0

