3.4. Baseline Definitions

To assess the dual nature of efficacy parameters, two efficacy baseline definitions will be used.

- Placebo-controlled period baseline (PCPB): is defined as the last available measurement prior to the first dose of setmelanotide or placebo. PCPB will be used for efficacy analysis based upon 14 weeks of treatment with either setmelanotide or placebo.
- Active treatment baseline (ATB): is defined as the last available measurement prior to the first dose of active setmelanotide. ATB will be used for efficacy analyses based upon ~52 weeks of treatment.

For safety, including key laboratory (e.g. hematology and chemistry) parameters, the last measurement prior to the first dose of setmelanotide or placebo will be used as the baseline.

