3.6. Adjustments for Covariates

No formal statistical analyses that adjust for possible covariate effects are planned.

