By nature of the study design (as introduced above in Section 1.2), a small percentage of patients who are randomized into the placebo arm may have less than ~52 weeks of setmelanotide treatment by the timing of the primary analysis (when the last patient enrolled has completed Period 2). Hence, the primary analysis will include a multiple imputation (MI) model (SAS PROC MI) that will be used to impute the measurements for patients with less than ~52 weeks of setmelanotide treatment to a timepoint that approximates 52 weeks of setmelanotide treatment. The final multiple imputed datasets will be analyzed using Rubin's rule (with SAS PROC MIANALYZE).

Due to the relatively small number of observation (i.e., number of patients) and large number of the visits (~15 protocol specified visits), there may not be enough observations to fit regression models in the multiple imputation. Therefore, protocol specified visits will be combined as appropriate, and the averaged values (across the combined visits) per the new derived Visit Categories (VC) will be used in the regression in the multiple imputation (SAS PROC MI). The multiple imputation model will contain the following new visit categories (VC) derived as follows:

- VC1=Average (V1, V2)
- VC2=Average of Scheduled Visits between VC1 and VC3
- VC3=Visit Occurring Closest to Day 98/14 Weeks within analysis window
- VC4=Average of Scheduled Visits between VC3 and VC5
- VC5=Visit Occurring Closest to Day 365/52 Weeks within analysis window
- VC6=Average of Scheduled Visits between VC5 and VC7

27

• VC7=Visit Occurring Closest to Day 462/66 Weeks within analysis window

Note, Early Termination visits will be treated as scheduled visits and may slot into any VC as fits criteria. Further, imputation of weight for 52 week analysis will focus on VC5 (for subjects initiated on active treatment) and VC7 (for subjects initiated on placebo) as these VCs are identified similarly, if not exactly, as the true timepoint would be identified, if it were not missing.

The above planned combination of the visits may be adjusted if the model cannot be fitted due to small sample size. Details will be defined in the ADRG.

Once VCs are identified, they will be time aligned by treatment arm before multiple imputation occurs.

That is, subjects initially randomized into the active treatment arm will have:

- VC1
- VC2
- VC3
- VC4
- VC5 (52 Weeks on Active Treatment)

While subjects initially randomized into the placebo arm will have:

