3.10.3. Approach on Missing Value in ~14-Week Placebo-Controlled, Double-Blinded Period (Period 1)

Patients may have missing values in Period 1 for many reasons such as drop out, early discontinuation, missed visits, or AEs etc. Missing values in this period will be imputed with a similar MI approach as 52 week analysis as defined in the primary imputation approach.

However, as this analysis revolves around 14 week timepoint, VC3 will be the focus of the imputation model. VC1, VC2, and VC3 will used in the multiple imputation model (SAS PROC MI) for 14 week timepoint with treatment group as a class factor. A sensitivity analysis may be conducted based on treatment failure approach on the missing value imputation for this period as appropriate.

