4.3.3. Other Secondary Efficacy Analyses of the 14-week, placebo-controlled period

These analyses will be performed on patients in the PCS population, (i.e., on data from the ~14-week, placebo-controlled, randomized, double-blinded period, or Period 1). Where applicable, the secondary endpoint will be compared against the null hypothesis for each of the 100 imputed datasets. The outcomes from the 100 imputed datasets will be combined using Rubin's Rule to provide a p-value and corresponding confidence interval as appropriate.

Body Weight Percent Change from Baseline at 14 Weeks:

The analysis on this secondary endpoint will be a between-group comparison to investigate if setmelanotide-treated patients (\geq 12 years old) exhibit a greater decrease in percent change in body weight from baseline at \sim 14 weeks of therapy, as compared to placebo-treated patients.

This analysis will be based on a two-sample t-test for each of the 100 imputed datasets. The outcomes from the 100 imputed datasets will be combined using Rubin's Rule to provide a p-value and corresponding confidence intervals. This will be evaluated at a 1-sided, 0.025 significance level.

Sensitivity analyses based on PP at EOP1 and CS may be provided.

Descriptive statistics for the change and percent change from baseline in body weight (kg) may be presented for the PCS population by visit by randomized treatment.

Daily Hunger Score Percent Change from Baseline at 14 Weeks

The analysis on this secondary endpoint will be a between group comparison to investigate if setmelanotide-treated patients exhibit a greater improvement from baseline at ~14 weeks of therapy in weekly average of daily hunger scores, as compared to placebo-treated patients. This analysis will be based on a two-sample t-test for each of the 100 imputed datasets. The outcomes from the 100 imputed datasets will be combined using Rubin's Rule to provide a p-value and corresponding confidence intervals. This will be evaluated at a 1 sided, 0.025 significance level.

Prior to analysis, daily hunger scores for each of the 3 hunger assessments will be averaged separately by week, as outlined above. Sensitivity analyses based on PP at EOP1 and CS may be provided.

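### The Week-14 hunger comparison with placebo leaves out baseline hunger as a covariate, giving up precision if baseline and Week-14 scores correlate at about 0.5 or less

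*SAP*

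**What the plan says.** SAP 3.6 is one sentence: "No formal statistical analyses that adjust for possible covariate effects are planned". SAP 4.3.3 applies this to both Week-14 endpoints, weight and hunger: "This analysis will be based on a two-sample t-test for each of the 100 imputed datasets". Results are pooled by Rubin's rule and "evaluated at a 1-sided, 0.025". The hunger endpoint in SAP 1.3.5 is "Mean percent change from baseline in the weekly average of the daily hunger score", compared with placebo in patients aged 12 or over.

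Baseline is used in two ways. First, it is the denominator of the percent change; SAP 3.4 says "PCPB will be used for efficacy analysis based upon 14 weeks of treatment with either setmelanotide or placebo". Second, SAP 3.10.3 puts the averaged screening and Day 1 value (visit category VC1, defined in SAP 3.10.1) into the Week-14 imputation model, with treatment as a class factor. That second use affects missing values only.

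Baseline hunger is secured before randomisation: a footnote to the schedule in SAP 1.3.4 requires the diary on "at least four of the seven days prior to V2". Randomisation (SAP 1.3.2) is stratified by age group and disease, not by hunger. The sensitivity analyses named for Week 14 in SAP 4.3.3, 4.3.4 and Table 3 (per-protocol, completers, 3 of 7 days, treatment failure) add no baseline term.

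**The concern.** Dividing by baseline does not remove dependence on baseline. When a self-reported score is only moderately correlated over time, patients who start high tend to fall and patients who start low tend to rise, whatever they receive. Percent change is then negatively related to baseline. Part of its variance could be removed by a covariate already in hand, and a chance difference in baseline hunger between arms carries into the estimated effect.

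Period 1 is the only randomised, blinded comparison in the trial, and Protocol 3.4 relies on the placebo period particularly for hunger. The pivotal cohort has 38 patients of all ages (SAP 1.1.1), so at most about 19 per arm. The analysed number is smaller, because the test is limited to patients aged 12 or over and Protocol 6.4.5.1 further limits self-report to those able to assess their own hunger. At that size chance imbalance is to be expected.

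**Working it through.** **The plan's own figure.** No power figure is given for Week 14. The only one in the documents is for the one-sample primary test (n = 7, 66% against 10%). Exact binomial with success at 3 or more of 7 has size 0.0257 and power 95.1%, matching the stated ~95% at one-sided 0.05. This has no bearing on the Week-14 comparison.

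**Inputs from the documents.** Two-sample t-test, one-sided 0.025, 1:1 allocation, percent change from baseline, 38 patients in total.

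**Assumed inputs.** A 0-10 scale with baseline mean 7 and baseline limited to 3-10. Scenario A: SD 1.8, drug lowers hunger by 25% of baseline, 14 per arm. Scenario B: SD 1.5, drug lowers hunger by 1.5 points, 7, 10 or 15 per arm. The baseline-to-Week-14 correlation ρ runs from 0.3 to 0.85.

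**Step 1, closed form for absolute change.** With equal SD σ at both times, the per-patient variance is 2σ²(1−ρ) for the t-test on change and σ²(1−ρ²) for ANCOVA. The ratio is (1+ρ)/2: 0.65 at ρ = 0.3, 0.75 at 0.5 and 0.85 at 0.7. The planned outcome is percent change, for which this is only a guide, so it was simulated (5,000 trials per setting in scenario B).

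**Step 2, percent change.** Variance of the ANCOVA estimate divided by that of the t-test, then power from t-test to ANCOVA:

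| ρ | A, 14 per arm | B, 15 per arm | B, 10 per arm | B, 7 per arm |
|---|---|---|---|---|
| 0.3 | 0.67-0.73; 48-50% to 61-63% | 0.72; 62% to 74% | 0.73; 43% to 54% | 0.75; 32% to 38% |
| 0.5 | 0.78-0.83; 61-64% to 71-72% | 0.85; 77% to 82% | 0.84; 57% to 63% | 0.89; 42% to 45% |
| 0.7 | 0.88-0.93; 83-84% to 86% | 0.97; 93% to 94% | 0.97; 78% to 78% | 0.99; 61% to 61% |
| 0.85 | 0.97 | 1.02; no gain | 1.03; 97% to 96% | 1.05; 89% to 85% |

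Ranges under A are from repeated runs. The figures move by a few points with the treatment of values beyond the ends of the scale.

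**Step 3, chance imbalance at ρ = 0.5.** Shift in the unadjusted estimate = slope on the baseline difference × chance SD of that difference.
- B, 15 per arm: 6.6 percentage points per point × 0.52 points ≈ 3.4, say 3.5. The effect is 22.5 points, so this is 3.5/22.5 ≈ 16% of it.
- A, 14 per arm: about 9 × 0.58 ≈ 5.
- With ANCOVA the slope is about 0 in both.

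**Step 4, type I error.** With no true effect and ρ = 0.5 (B, 7 to 15 per arm), the t-test rejects 2.3-2.5% of the time and ANCOVA 2.3-2.8%. Both are close to nominal.

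**Step 5, weight.** With an assumed mean of 115 kg and SD of 25 kg, the variance ratio for percent change in weight is 1.02-1.05; a separate run gave 0.96-1.04. No material gain is shown.

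**The case against.** The strongest defence is that the unadjusted test is pre-specified, openly stated and valid. Under randomisation the t-test is unbiased on average, and its interval already allows for chance imbalance. A reader might infer that the plan ignores baseline, or that the result is biased or its error rate inflated. The documents support neither: baseline forms the outcome and enters the imputation model, and Step 4 shows the nominal rate is kept. What remains is efficiency, plus the movement of the estimate when a particular imbalance occurs.

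The second defence is that the gain depends on a correlation nobody has stated. This stands. The outcome is a weekly average, not a single reading, which could push the correlation up. On the other side, a week counts with 1 recorded day of 7 (SAP 4.3.2) and the Week-14 window is ±4 weeks (SAP 3.11.2), which could push it down. The documents do not settle it.

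Third, the hunger sample may be small: patients who cannot self-assess because of impaired cognition use a caregiver instrument instead. At 7 per arm the power gain is only 6, 3 and 0 points at correlations of 0.3, 0.5 and 0.7, and at 0.85 there is a 4-point loss.

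Fourth, this is an other-secondary endpoint outside the key-secondary hierarchy. That also stands and limits the weight of the point.

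**Conclusion.** The point holds for hunger, as a nearly free improvement rather than an error. If the baseline-to-Week-14 correlation is 0.5 or lower, leaving out baseline hunger gives up roughly 15-35% of variance with 14 to 15 per arm. At 0.7 the figure is 3-12%, and at 0.85 there is essentially nothing to gain. The estimate also moves with chance imbalance, by about 3.5 to 5 percentage points per chance SD at a correlation of 0.5. All of this rests on an assumed scale, mean, SD, effect, correlation and sample size.

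Two wider readings should be resisted. One is that the Week-14 weight test has the same fault; Step 5 shows no material gain there. The other is that trial success is at risk. The primary analysis in SAP 4.3.1 is a one-sample responder test against 10% and has no between-arm comparison to adjust.

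**What to change.** Before unblinding, and before any Period 1 result from SAP 4.7 is released, amend SAP 3.6 and 4.3.3:

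- Analyse Week-14 percent change in each weekly average hunger score by ANCOVA, with treatment and the PCPB weekly average of the same hunger item as covariate.
- Fit the model in each of the 100 imputed datasets and pool by Rubin's rule, at the same one-sided 0.025 level.
- Keep the two-sample t-test as a sensitivity analysis.
- State how the baseline weekly average is formed. SAP 3.4 says only that PCPB is the last available measurement; the seven days before V2, already required for the diary, would serve.
- Leave the percent change in weight test as it is.

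The cost is a change of wording, one model term and one degree of freedom (2n−2 to 2n−3 for n per arm). No new data are needed, and the endpoint does not change. If the correlation is very high and the sample very small, expect no gain or a slight loss. Timing matters because an adjustment chosen after an imbalance has been seen carries little credibility.

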3.7. Multiple Comparisons/Multiplicity

No multiplicity adjustments are required for the primary analysis as this study has only 1 primary endpoint. This controls the overall alpha at 0.025, 1-sided.

There are multiple key secondary efficacy endpoints planned in the study (see Section 1.3.5.1). However, based on the rarity of this disease, and the small number of patients to be enrolled in this study, the ability to use extremely rigorous statistical approaches to address multiplicity for these secondary endpoints is limited. Therefore, for publication, nominal-p-values will be used to interpret *each endpoint separately* in this small study. The Sponsor acknowledges that this approach may increase the probability of potential Type 1 error for the *set* of key secondary efficacy endpoints being analyzed. While this SAP does not envision multiplicity adjustments in this study, the Sponsor has pre-specified a step-down procedure (a hierarchical order of testing for the key secondary efficacy endpoints) to control Type-1 error, if needed for any purpose. The key secondary endpoints are presented according to the Sponsor-specified hierarchical order in Section 4.3.2.

3.8. Subgroups

3.8.1. Subgroup Analysis by Disease Type

Subgroup analysis by disease type (e.g., BBS and AS; clinically defined or genetically defined) on primary efficacy and key secondary efficacy endpoints will be summarized separately. Analysis on the secondary endpoints, i.e., mean percent change of weight and hunger score at ~14 week from baseline, will be conducted for each disease type. A 1-sided p-value and corresponding 95% 2-sided confidence interval will be provided. Please note that the study is not powered for individual subgroups, but powered based on the overall number of the pooled patients across disease types. Thus, the p-values for the subgroup analyses are exploratory and should be interpreted with caution and clinical judgement.

Please note that patients who enter the study based solely on clinical criteria (even if later they are confirmed by genetic testing) will define the "clinically-defined" subgroup. Therefore, appropriate efficacy analysis by disease type subgroups will be performed based on clinically defined subgroup criteria.

3.8.2. Subgroup Analysis of Pediatric Subjects

Subgroup analysis on pediatric populations will be conducted. The subgroup analysis may be performed based on the following age (at informed consent) categories:

- Patients <12 years old (i.e., 6-11 years old)
- Patients <17 years old (i.e., 6-16 years old)

Analysis of the primary efficacy and key secondary efficacy endpoints may be repeated for these two subsets and presented separately. Between-treatment group analysis (setmelanotide vs placebo) within each age category on the secondary endpoints, i.e., mean percent change of weight and hunger score at ~14 week from baseline, may be conducted.

The number of the pediatric patients in the pivotal cohort may be small, so these subgroup analyses may combine pediatric patients from both pivotal and supplemental cohorts as necessary.

A 1-sided p-value and corresponding 95% 2-sided confidence interval will be provided. Please note that the study is powered based on the overall number of the pooled patients, thus the p-values for the subgroup analysis are exploratory and should be interpreted with caution and clinical judgement.

3.9. Withdrawals, Dropouts, Loss to Follow-up

Patients will be informed that they have the right to withdraw their consent to participate in the study at any time for any reason, without prejudice to their medical care. The Investigator also has the right to withdraw patients from the study, after discussion with the Sponsor, for any of the following reasons:

- Non-adherence to study drug regimen or protocol requirements.
- Non-compliance with instructions or failure to return for follow-up.

If a patient is withdrawn or discontinued from the study, the primary reason for withdrawal from the study is to be recorded in the source documents/electronic case report form (eCRF).

Any patient that discontinues treatment prior to completing the study should be strongly encouraged to complete all remaining visits and procedures as outlined in the SOA, even if they are no longer receiving study drug.

In case of discontinuation, all AEs should be followed as described in Protocol Section 7.4; any skin AEs should continue to be followed, if at all feasible, for ~60-90 days to confirm near or complete resolution (as has been shown in previous studies).

The Sponsor will provide support for patient and caregiver travel, will make available visiting home health care professionals, and any other necessary logistical support to ease the burden on the patient to facilitate compliance.

3.10. Missing, Unused, and Spurious Data

In general, there will be no substitutions made to accommodate missing data points. All data recorded on the CRF will be included in data listings that will accompany the CSR.

When tabulating AE data, partial dates will be handled to more accurately determine whether an event was treatment-emergent.

AE start dates that are missing or incomplete will be handled as follows:

- (1) Missing Day Only
 - If the month and year are the same as the month and year of the first dose date, the first dose date will be used.
 - If the month and year are before the month and year of the first dose date, the last day of the month will be assigned to the missing day.
 - If the month and year are after the month and year of the first dose date, the first day of the month will be assigned to the missing day.
- (2) Missing Day and Month
 - If the year is the same as the year of the first dose date, the first dose date will be used.
 - If the year is prior to the year of the first dose date, December 31 will be assigned to the missing fields.
 - If the year is after the year of first dose date, January 1 will be assigned to the missing fields.

26

(3) Missing Day, Month, and Year

• The first dose date will be used.

If the stop date is non-missing and the imputed start date is after the stop date, the stop date will be used as the start date. If the stop date is missing and the imputed start date is after a patient's date of discontinuation, the date of discontinuation will be used.

AE stop dates that are missing or incomplete will be handled as follows:

- (1) Missing Day Only
 - The last day of the month will be assigned as the missing day.
- (2) Missing Day and Month
 - December 31 will be assigned to missing fields.
- (3) Missing Day, Month, and Year
 - The event will be regarded as ongoing.

If the start date is non-missing and the imputed stop date is before the start date, the start date will be used. If the death date is available and the imputed stop date is after the death date, the death date will be used.

3.10.1. Analyses of Patients Who were Initially Randomized into Placebo Arm with Less than ~1 Year of Data at

By nature of the study design (as introduced above in Section 1.2), a small percentage of patients who are randomized into the placebo arm may have less than ~52 weeks of setmelanotide treatment by the timing of the primary analysis (when the last patient enrolled has completed Period 2). Hence, the primary analysis will include a multiple imputation (MI) model (SAS PROC MI) that will be used to impute the measurements for patients with less than ~52 weeks of setmelanotide treatment to a timepoint that approximates 52 weeks of setmelanotide treatment. The final multiple imputed datasets will be analyzed using Rubin's rule (with SAS PROC MIANALYZE).

Due to the relatively small number of observation (i.e., number of patients) and large number of the visits (~15 protocol specified visits), there may not be enough observations to fit regression models in the multiple imputation. Therefore, protocol specified visits will be combined as appropriate, and the averaged values (across the combined visits) per the new derived Visit Categories (VC) will be used in the regression in the multiple imputation (SAS PROC MI). The multiple imputation model will contain the following new visit categories (VC) derived as follows:

- VC1=Average (V1, V2)
- VC2=Average of Scheduled Visits between VC1 and VC3
- VC3=Visit Occurring Closest to Day 98/14 Weeks within analysis window
- VC4=Average of Scheduled Visits between VC3 and VC5
- VC5=Visit Occurring Closest to Day 365/52 Weeks within analysis window
- VC6=Average of Scheduled Visits between VC5 and VC7

27

• VC7=Visit Occurring Closest to Day 462/66 Weeks within analysis window

Note, Early Termination visits will be treated as scheduled visits and may slot into any VC as fits criteria. Further, imputation of weight for 52 week analysis will focus on VC5 (for subjects initiated on active treatment) and VC7 (for subjects initiated on placebo) as these VCs are identified similarly, if not exactly, as the true timepoint would be identified, if it were not missing.

The above planned combination of the visits may be adjusted if the model cannot be fitted due to small sample size. Details will be defined in the ADRG.

Once VCs are identified, they will be time aligned by treatment arm before multiple imputation occurs.

That is, subjects initially randomized into the active treatment arm will have:

- VC1
- VC2
- VC3
- VC4
- VC5 (52 Weeks on Active Treatment)

While subjects initially randomized into the placebo arm will have:

- VC3
- VC4
- VC5
- VC6
- VC7 (52 Weeks on Active Treatment)

Monotone regression will then be used to impute the missing values, assuming proper missingness structure. The monotone regression method will impute 100 datasets. A seed of 2187 has been randomly generated and will be used.

Fully conditional specification (FCS) regression may be used in the case that monotone regression is deemed not appropriate.

Daily hunger scores will have weekly average hunger score calculated and these weekly averages mapped to Visit Categories with the same algorithm as above.

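### The SAP 3.10 rule that resets an imputed adverse event start date to the date of discontinuation acts only on events recorded as starting after discontinuation, so it always substitutes a date that the record contradicts (minor, safety tabulation only)

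*SAP*

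**What the plan says.** SAP section 3.10 gives the rules for incomplete adverse event start dates. Their stated purpose is a better decision on whether an event is treatment-emergent.

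For a missing day there are three cases:
- Month of first dose: "If the month and year are the same as the month and year of the first dose date, the first dose date will be used".
- Earlier month: "If the month and year are before the month and year of the first dose date, the last day of the month will be assigned".
- Later month: "If the month and year are after the month and year of the first dose date, the first day of the month will be assigned".

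When day and month are both missing, the pattern repeats by year. For the year of first dose, "If the year is the same as the year of the first dose date, the first dose date will be used". An earlier year gives 31 December, and a later year gives 1 January. A fully missing date becomes the first dose date.

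Two corrections follow. The first is "If the stop date is non-missing and the imputed start date is after the stop date, the stop date will be used as the start". The second is the rule at issue: "If the stop date is missing and the imputed start date is after a patient's date of discontinuation, the date of discontinuation will be used". The second sentence does not say which date is replaced. Read in parallel with the first, it is the start date. Under the stop-date rules of the same section, a fully missing stop date means that the event is ongoing.

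SAP section 3.9 (and protocol section 4.5) urges patients who stop treatment to "complete all remaining visits and procedures as outlined in the SOA, even if they are no longer receiving study drug".

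**The concern.** A cap of this kind is useful when imputation can push a date past a limit that the true date respects. Here the imputed date for any onset after the first-dose month or year is already the earliest day compatible with the record. If even that day is after discontinuation, the record itself says that the event began after discontinuation, and the cap then discards what is known.

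Patients who stop drug are encouraged to keep attending visits, so new onsets after the last dose can be recorded. Moving such an onset back to the date of discontinuation can change how it is tabulated: as on-treatment rather than off-drug, or in an earlier period of the study. SAP section 4.7 plans safety summaries for Period 1 alone. A patient who stops drug in Period 1 and stays in follow-up could have a later onset pulled into that period.

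**Working it through.** **When can the cap act?** Let F be the date of first dose and D the date of discontinuation, with D on or after F. Going through each start-date case in SAP 3.10:

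| Recorded start | Imputed start | Can it be after D? |
|---|---|---|
| Month of F | F | No |
| Month before that of F | Last day of that month, before F | No |
| Month after that of F | First day of that month | Only if the whole month is after D |
| Year of F | F | No |
| Year before that of F | 31 December, before F | No |
| Year after that of F | 1 January | Only if the whole year is after D |
| Nothing recorded | F | No |

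The cap therefore acts only when the recorded month or year lies wholly after D.

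**Check by enumeration.** The rules were coded as written. They were run over first-dose dates across a year, D from 0 to 462 days after F, and true onset from 60 days before to about 640 days after F, giving 1,891,000 cases for each type of incomplete date. Apart from the missing-stop-date condition, the cap would act in 1,054,080 month-and-year cases, 620,085 year-only cases and 0 fully missing cases. These counts reflect the grid and are not expected rates. The informative results are two zeros: in no case was the recorded month or year other than strictly after that of D, and in no case was the true onset on or before D.

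**Worked example.** F = 10 March 2019, D = 20 August 2019, event ongoing.
- August 2019, day unknown: imputed 1 August; no reset.
- September 2019, day unknown: imputed 1 September; reset to 20 August, 12 days earlier.
- 2019 only: imputed 10 March; no reset.
- 2020 only: imputed 1 January 2020; reset to 20 August 2019, 134 days earlier (11 + 30 + 31 + 30 + 31 + 1).

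For an onset in the month just after D, the shift is 1 to 31 days. It is longer for later months. If D is the drug-stop date, a patient who stops at Week 10 and is followed to Week 66 could have an onset moved by up to 66 − 10 = 56 weeks.

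**Contrast with the stop-date correction.** With F = 10 March, onset in March with the day unknown, and stop on 5 March, the imputed start of 10 March is impossible. Resetting it to 5 March repairs a true artefact. The discontinuation cap has no such case.

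**Uneven dating.** Take D = 10 April and three events that all began in September:
- A complete start date of 3 September is kept.
- September, day unknown, with a later stop date, becomes 1 September.
- September, day unknown, still ongoing, becomes 10 April, which is 144 days before 1 September (20 + 31 + 30 + 31 + 31 + 1).

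**How many events?** The documents give no rates, so these are assumptions: 4 to 8 of the 38 pivotal patients discontinue, each has 1 to 3 off-drug events, and 5% to 10% of start dates are incomplete.
- Low: 4 × 1 × 0.05 = 0.2 events. High: 8 × 3 × 0.10 = 2.4 events.
- The cap also needs an ongoing event. If, for illustration, 30% are ongoing: 0.2 × 0.3 = 0.06 and 2.4 × 0.3 = 0.72.
- It further needs the recorded month or year to be wholly after D, which lowers the count again.

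One patient in 38 is 1/38 = 2.6 percentage points. An incidence would move by that much only if the event's classification changes and the patient is not already counted for the same event.

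**The case against.** A reader might infer that every use of the cap turns an off-drug event into an on-treatment one. The documents do not support that. The available text contains no definition of treatment-emergent; it may be in material not shown, so its absence is not a fault of the plan. The imputation rules all pivot on the first dose date, and none uses a last-dose date. If treatment-emergent means any onset on or after first dose, or within a post-dose window that already covers the true onset, the label does not change. SAP 3.9 also speaks of discontinuing both treatment and the study. If the cap refers to study exit, the reset date may itself be well after the last dose.

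Three further points have force. The date rules apply when adverse events are tabulated, and everything on the case report form stays in the listings, so the recorded partial date is not lost. The skin follow-up of about 60 to 90 days concerns resolution of existing events and is no evidence of new onsets; only the request to attend remaining visits supports those. And an onset month after study exit could be an entry error, in which case a cap looks like a plausibility guard.

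The last point does not rescue the rule. A date thought to be wrong should be queried, which is what protocol section 9.6.5 provides for. Silent replacement hides the discrepancy. The other points limit the consequence but leave the logic intact: the cap acts only where the record places onset after discontinuation.

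**Conclusion.** The sentence is wrong as written, and the matter is minor. Provided the recorded month and year are correct, every use of the cap replaces a compatible date with an incompatible one, which works against the section's own aim. That follows from the imputation rules alone, under either meaning of discontinuation.

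The effect on classification is a possibility, not a certainty. If discontinuation means stopping drug and the on-treatment period ends at or near last dose, an off-drug onset would be counted as on-treatment. For a patient who stops drug during Period 1, it could enter the Period 1 safety summaries. Under other definitions only the date changes.

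On the assumed rates, probably fewer than one or two events are affected. Only adverse event timing and tabulation are involved; the efficacy analyses, alpha and sample size are not touched.

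**What to change.** Delete the sentence from SAP 3.10 and the matching line from the derivation program. Keep the imputed first of the month, or 1 January, when the recorded month or year is after discontinuation, and apply the SAP's own treatment-emergent definition to that date. Send any adverse event month or year recorded after study exit to data query under protocol section 9.6.5 instead of overwriting it. Because the cap never corrects an imputation artefact, nothing is lost by removing it. The cost is one sentence, one line of program and the occasional query; no new data collection is needed.
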